3.2 Efficacy Variables

3.2.1 Objective response rate (ORR)

ORR (per RECIST 1.1, using Investigator assessments) is defined as the percentage of patients with at least 1 investigator-assessed visit response of CR or PR that is subsequently confirmed on another scan not less than 4 weeks after visit observed response. Data obtained up until progression, or the last evaluable assessment in the absence of progression, will be included in the assessment of ORR. Patients who go off treatment without progression, receive a subsequent therapy, and then respond will not be included as responders in the ORR.

ORR is primary endpoint of dose-expansion phase.

3.2.2 Progression-free survival (PFS)

Progression free survival (per RECIST 1.1, as assessed by the site Investigator) will be defined as the time from the date of first dose of study treatment until the date of objective disease progression or death (by any cause in the absence of progression) regardless of

whether the patient withdraws from study therapy or receives another anti-cancer therapy prior to progression (i.e. date of PFS event or censoring – date of first dose + 1). Patients who have not progressed or died at the time of analysis will be censored at the time of the latest date of assessment from their last evaluable RECIST 1.1 assessment. However, if the patient progresses or dies after 2 or more missed visits, the patient will be censored at the time of the latest evaluable (RECIST 1.1) assessment prior to the 2 missed visits (Note: NE visit is not considered a missed visit).

Given the scheduled visit assessment scheme (i.e. eight-weekly (+/-1 week) for the first 12 months with the option of moving to every 16 weeks \pm 1 week thereafter (for those with a sustained objective response), until clinical progression/deterioration) the definition of 2 missed visits will change over time on a per patient basis.

If the previous (RECIST 1.1) assessment is between study day 49 (i.e. week 7) and less than the last assessment on an 8-weekly schedule then two missed visits will equate to 18 weeks since the previous RECIST 1.1 assessment, allowing for early and late visits (i.e. 2 x 8 weeks + 1 week for an early assessment + 1 week for a late assessment = 18 weeks). If the two missed visits occur over the period when the scheduled frequency of RECIST 1.1 assessments changes from eight-weekly to sixteen-weekly this will equate to 26 weeks (i.e. take the average of 8 and 16 weeks which gives 12 weeks and then apply same rationale, hence 2 x 12 weeks + 1 week for an early assessment + 1 week for a late assessment = 26 weeks). Once the scheduling changes to sixteen-weekly assessments, two missing visits will equate to 34 weeks (i.e. 2 x 16 weeks + 1 week for an early assessment + 1 week for a late assessment = 34 weeks).

If a patient has no evaluable visits or does not have baseline data, they will be censored at day 1 unless they die within 2 visits of baseline (16 weeks plus 1 week allowing for a late assessment within the visit window) then they will be treated as an event with date of death as the event date.

The PFS time will always be derived based on scan/assessment dates not visit dates.

RECIST 1.1 assessments/scans contributing towards a particular visit may be performed on different dates. The following rules will be applied:

- For Investigator assessments, date of progression will be determined based on the earliest of the assessment/scan dates of the component that triggered the progression.
- When censoring a patient for PFS the patient will be censored at the latest of the dates contributing to a particular overall visit assessment.

Note: For TLs, only the latest scan date is recorded out of all scans performed at that assessment for the TLs and similarly for NTLs, only the latest scan date is recorded out of all scans performed at that assessment for the NTLs.

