Radiological efficacy assessments ^u	X	On-study efficacy assessments occur every 8 weeks ± 1 week (always relative to the date of first dose), until radiological progression plus an additional regularly scheduled follow-up scan. This schedule MUST be followed regardless of any delays in dosing. For patients who achieve an objective response (CR, PR) or stable disease, and for whom the response is still evident at 12 months, subsequent tumor assessments are to occur every 16 weeks. Unscheduled assessments can be performed at any time during the study, as clinically indicated, based on signs and symptoms							8.1

Note: All assessments on treatment days are to be performed prior to infusion, unless otherwise indicated.

Note: Patients who restart combination therapy (having subsequently progressed on durvalumab monotherapy following the completion of 4 months of combination therapy) should complete the same assessments starting from Cycle 1 Day 1 of the dose-expansion phase, with the exception of PK, ADA, tumor biopsies, blood for CCI analysis, blood for CCI sequencing, and CCI.

^a Visit windows are relative to the first day of each cycle.

^b Written informed consent/assent and any locally required privacy act document authorization must be obtained prior to performing any protocol-specific procedures, including screening/baseline evaluations. If laboratory or imaging procedures were performed for alternate reasons prior to signing consent, these can be used for screening purposes with consent of the patient's parent(s)/legally authorized representative(s). However, all screening laboratory assessments must have been obtained within 28 days of Cycle 1 Day 1 and imaging/staging examination results must have been obtained within 21 days of Cycle 1 Day 1. The unique enrollment code will be obtained after ICF signature, through the IRT/RTSM.

^c Any clinically significant abnormalities detected require a confirmatory ECG result.

^d Tobacco use will be collected at the Investigator's discretion.

^e Serum or plasma clinical chemistry (including LFT monitoring) and hematology may be performed more frequently if clinically indicated.

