8.1 Efficacy assessments

Efficacy assessments of ORR, duration of response (DoR), DCR, and PFS will be derived (by AstraZeneca) using the response criteria defined below. Overall survival will also be assessed for each individual patient.

Tumor assessments will be done in accordance with the type of tumor: NB ([Appendix F](#)), other solid tumors ([Appendix E](#)).

Radiological assessments will be made following routine clinical practice procedures during screening and then every 8 weeks (relative to the date of Cycle 1 Day 1), until radiological progression. For patients who achieve an objective response (CR, PR) or stable disease and for whom the response is still evident at 12 months, subsequent tumor assessments are to occur every 16 weeks. Unscheduled assessments can be performed at any time during the study, as clinically indicated, based on signs and symptoms. Disease progression requires confirmation, the confirmatory scan should occur preferably at the next scheduled visit and no earlier than 4 weeks after the initial assessment of PD in the absence of clinically significant deterioration. Treatment will continue between the initial assessment of progression and confirmation for progression.

Tumor assessments will be made during screening/baseline and at regular (follow-up) intervals during study treatment. Pelvic imaging is recommended only when primary or metastatic disease in the pelvic region is likely. Any other areas of disease involvement should be additionally imaged based on the signs and symptoms of individual patients. It is important to follow the tumor assessment schedule as closely as possible (refer to the SoAs). If an unscheduled assessment is performed (eg, to investigate clinical signs/symptoms of progression) and the patient has not progressed, every attempt should be made to perform the subsequent assessments at the next scheduled visit. Treatment continues until clinical progression/deterioration or confirmed radiological progression, and scanning/tumor assessments continue throughout treatment until radiological progression plus an additional follow-up scan (if clinically feasible).

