3 PRIMARY AND SECONDARY VARIABLES

3.1 Derivation of visit tumor responses

The analysis of the primary endpoint, ORR, and the analyses of the secondary endpoints, PFS, DoR, and DCR, will be based on the site Investigator assessments using the following criteria

Table 5 Criteria for Investigator assessments

Type of cancer	Criteria
Solid Tumors	
SARCOMA and STO	RECIST 1.1 (see CSP Appendix E)

All RECIST 1.1, whether scheduled or unscheduled, will be included in the calculations. This is also regardless of whether a patient discontinues study treatment or receives another anticancer therapy.

Baseline will be assessed within the 21 days prior to first dose of study treatment and ideally as close as possible to the start of study treatment. Assessments are performed every 8 weeks (relative to the date of first dose of study treatment) in the first instance. For patients who achieve an objective response or stable disease, and for whom the response is still evident at 12 months, subsequent tumor assessments are to occur every 16 weeks \pm 1 week until disease progression.

If an unscheduled assessment is performed, and the patient has not progressed, every attempt should be made to perform the subsequent assessments at their scheduled visits. This schedule is to be followed in order to minimise any unintentional bias caused by some patients being assessed at a different frequency than other patients.

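### SAP 3.2.2 omits stable-disease patients from the 16-weekly scan schedule, so a progression or death after one missed scan could be censored as two missed visits

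*SAP*

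**What the plan says.** Two parts of the plan say who moves from 8-weekly to 16-weekly scans after 12 months, and they differ.

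- SAP 3.2.2, which sets the PFS censoring rule, describes 8-weekly scans for the first 12 months "with the option of moving to every 16 weeks" "thereafter (for those with a sustained objective response), until clinical progression/deterioration".
- SAP 3.1 gives the longer interval to a wider group: "For patients who achieve an objective response or stable disease, and for whom the response is still evident at 12 months".
- Protocol Section 8.1 agrees with SAP 3.1: "For patients who achieve an objective response (CR, PR) or stable disease and for whom the response is still evident at 12 months". The schedules of activities in protocol Section 1.1 do too, for example Table 2: "For patients who achieve an objective response (CR, PR) or stable disease, and for whom the response is still evident at 12 months".

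The censoring rule in SAP 3.2.2 is that "if the patient progresses or dies after 2 or more missed visits, the patient will be censored" at the last evaluable assessment before the gap. What counts as two missed visits is then given in weeks, patient by patient:

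- 8-weekly schedule: "2 x 8 weeks + 1 week for an early assessment + 1 week for a late assessment = 18 weeks"
- across the change of schedule: "2 x 12 weeks + 1 week for an early assessment + 1 week for a late assessment = 26 weeks"
- 16-weekly schedule: 34 weeks, built the same way.

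Protocol Section 9.4.1.3 has the same rule without limits in weeks. SAP Section 6, which lists departures from the protocol, does not mention a narrower group for the 16-weekly schedule.

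**The concern.** The parenthesis sits in the sentence that introduces the missed-visit limits. Section 3.2.2 makes the switch optional and gives no other patient-level criterion for deciding who has switched. A programmer who takes schedule status from this section alone would leave a stable-disease patient on the 8-weekly schedule, and so under the 18-week limit, although that patient is scanned every 16 weeks as the protocol directs.

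A single missed scan would then look like two. A progression or death that the plan's own rule counts as an event would be censored at the earlier scan. Removing such an event makes late PFS look better than it was, in the part of the curve where few patients remain.

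**Working it through.** **Inputs.** Intervals of 8 and 16 weeks and a window of ±1 week (SAP 3.1 and 3.2.2); limits of 18, 26 and 34 weeks (SAP 3.2.2); PFS dated by scan, not by visit (SAP 3.2.2).

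**Step 1: reproduce the limits.** Limit = 2 × interval + 1 week early + 1 week late.

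- 8-weekly: 2 × 8 + 2 = 18
- change-over: 2 × (8 + 16)/2 + 2 = 26
- 16-weekly: 2 × 16 + 2 = 34

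All three match the SAP.

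**Step 2: compare real gaps with the limits.** With m scans missed, the nominal gap between two attended scans is (m + 1) × interval. Letting each scan fall anywhere within ±7 days gives 15 × 15 = 225 day combinations.

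| Schedule | Scans missed | Gap, weeks | Over 18 weeks | Over 34 weeks |
|---|---|---|---|---|
| 8-weekly | 1 | 14–18 | 0 of 225 | 0 of 225 |
| 8-weekly | 2 | 22–26 | 225 of 225 | 0 of 225 |
| 16-weekly | 0 | 14–18 | 0 of 225 | 0 of 225 |
| 16-weekly | 1 | 30–34 | 225 of 225 | 0 of 225 |
| 16-weekly | 2 | 46–50 | 225 of 225 | 225 of 225 |

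Each limit works on its own schedule: it passes one missed scan and catches two. The 18-week limit applied to 16-weekly scans catches one missed scan every time. With none missed, the gap peaks at exactly 18 weeks (1 of the 225 combinations). That is caught only if the rule is coded as 18 weeks or more, and SAP 3.2.2 does not say which inequality applies.

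**Step 3: change-over.** Scan at week 48, week 56 missed, progression at week 72 on the new schedule. The gap is 72 − 48 = 24 weeks (22 to 26 in window). It is over 18, so censored under the wrong limit. It is never over 26, so an event under the right one. Scan dates alone cannot settle the case: a patient still on 8-weekly scans with the same dates has missed two (weeks 56 and 64).

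**Step 4: reach into APF18.** Eighteen months is 1.5 × 365.25/7 = 78.3 weeks. After a last 8-weekly scan at week 48 or 56, the next two 16-weekly scans fall at weeks 64 and 80, or 72 and 88. Missing the first and progressing at the second puts the event at week 79 at the earliest, after 18 months. Censoring it removes no event before 18 months. It only takes the patient out of the risk set, which leaves APF18 unchanged or lower.

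APF18 can be overstated in two narrower situations:

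- the change-over case in step 3, with the event at week 72;
- a death or unscheduled scan after one missed visit but before about week 78. For example, with the last scan at week 56 and week 72 missed, an event between week 56 + 18 = 74 and week 78.3 would be lost.

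**The case against.** The strongest reply is that nothing in SAP 3.2.2 assigns the limits by response status. The 26-week and 34-week sentences depend on the scan frequency having changed, per patient. A stable-disease patient who has switched fits the 34-week sentence as written. The SAP amendment history points the same way: the missed-visit text was revised because the switch is optional, which suggests that the limit was meant to track the schedule. This stands. The error occurs only if status is taken from the parenthesis, but the section offers no other criterion, and the parenthesis points the wrong way for stable disease.

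Three stronger readings are tempting, and the documents do not support them.

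- *Patients with no missed scan would be censored.* Step 2 shows that they would not, if scans are in window and the inequality is strict. Nor is one day beyond the window generally enough. With the previous scan on time, a scan 8 days late gives 112 + 8 = 120 days, against a limit of 126. It passes 126 days only if the previous scan was also a full week early.
- *APF18 is generally overstated.* A progression found at the next regular 16-weekly scan after one missed scan falls after 18 months (step 4).
- *Two or three of 26 sarcoma patients are exposed.* This comes from 26 × 0.102 = 2.7, using the 12-month PFS that protocol Section 2.2.1 reports for another checkpoint inhibitor in a mixed paediatric population. It counts responders, whom the parenthesis already covers, and it ignores that a patient must also miss a scan. It also assumes that stage 2 opens; with 11 patients the same product is 1.1.

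It is also fair that applying 26 and 34 weeks by response status would create a new error. A patient still scanned 8-weekly could miss more than two visits and not be censored.

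**Conclusion.** The contradiction is real: SAP 3.2.2 disagrees with SAP 3.1 and with the protocol on who moves to 16-weekly scans. Its consequence is conditional and small. If schedule status is programmed from the parenthesis, a stable-disease patient on 16-weekly scans who misses one scan and then progresses or dies can be wrongly censored.

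Only PFS from about 12 months onward is affected, with APF18 limited to the situations in step 4. ORR, the primary endpoint of the dose-expansion phase, does not use this rule. Median PFS is very unlikely to change. DoR takes its end from PFS but concerns confirmed responders, who are already covered. The documents do not allow the number of exposed patients, or the size of the bias, to be computed. The conclusion rests on in-window scans and a strict inequality. It is a minor point, worth correcting because the correction is nearly free.

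**What to change.** In SAP 3.2.2:

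1. Replace the parenthesis with '(for those with an objective response or stable disease still evident at 12 months)'.
2. State that the 18-, 26- or 34-week limit follows each patient's actual scan schedule, so that a patient still scanned 8-weekly keeps 18 weeks. Because scan dates alone can be ambiguous (step 3), name the source from which the change of schedule is taken.
3. State that a limit is exceeded only when the gap is strictly greater than it.

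The cost is one phrase and two or three sentences in the SAP. No clinical procedure or scan schedule changes.

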3.2.3 Overall Survival (OS)

OS is defined as the time from the date of first dose of study treatment until death due to any cause regardless of whether the patient withdraws from study treatment or receives another anti-cancer therapy (i.e. date of death or censoring – date of first dose + 1). Any patient not known to have died at the time of analysis will be censored based on the last recorded date on which the patient was known to be alive. ('Date subject confirmed to be alive', recorded within the SURVIVE module of the eCRF).

Note: Survival calls will be made following the date of data cut off (DCO) for the analysis (these contacts should generally occur within 7 days of the DCO) and if patients are confirmed to be alive or if the death date is post the DCO date, these patients will be censored at the date of DCO. The status of ongoing, withdrawn (from the study) and "lost to follow-up" patients at the time of the final OS analysis should be obtained by the site personnel by checking the patient's notes, hospital records, contacting the patient's general practitioner and checking publicly-available death registries. In the event that the patient has actively withdrawn consent to the processing of their personal data, the vital status of the patient can be obtained by site personnel from publicly available resources where it is possible to do so under applicable local laws.

Note that for any OS analysis performed prior to the final OS analysis, in the absence of survival calls being made, it may be necessary to use all relevant eCRF fields to determine the last recorded date on which the patient was known to be alive for those patients still on treatment. The last date for each individual patient is defined as the latest among the following dates recorded on the eCRF:

- AE start and stop dates
- Admission and discharge dates of hospitalization
- Study treatment date
- End of treatment date
- Laboratory test dates
- Date of vital signs
- Date of ECG

- Disease assessment dates on RECIST/non-RECIST eCRF
- Start and stop dates of alternative anticancer treatment
- Date last known alive on survival status eCRF
- End of study date
- Date of any other safety data

If a patient is known to have died where only a partial death date is available, then the date of death will be imputed as the latest of the last date known to be alive +1 from the database and the death date using the available information provided:

- a. For Missing day only – using the 1st of the month
- b. For Missing day and Month – using the 1st of January

If there is evidence of death but the date is entirely missing, it will be treated as missing, i.e. censored at the last known alive date.

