3.2.8 Overall survival at 12 (OS12) and 24 (OS24) months

OS12 will be defined as the KM estimate of OS at 12 months. Similarly, OS24 will be defined as the KM estimate of OS at 24 months.

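### SAP 3.2.3 censors a patient known to be dead when the death date is entirely missing, an unexplained exception that would push OS, OS12 and OS24 upward if such a patient occurs

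*SAP*

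**What the plan says.** SAP 3.2.3 states the endpoint without qualification: "OS is defined as the time from the date of first dose of study treatment until death due to any cause". The general censoring rule follows: "Any patient not known to have died at the time of analysis will be censored based on the last recorded date" of known survival. Protocol 9.4.1.4 has the same censoring sentence and no exception for missing death dates.

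SAP 3.2.3 then sets two rules for incomplete death dates:

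- **Partial date.** The patient stays an event: "then the date of death will be imputed as the latest of the last date known to be alive +1 from the database" and the date built from what was recorded. When only the year is known, the built date is "For Missing day and Month – using the 1st of January".
- **No date at all.** The patient stops being an event: "evidence of death but the date is entirely missing, it will be treated as missing, i.e. censored at the last known alive date".

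SAP 3.2.8 takes both landmark estimates from the same curve: "OS12 will be defined as the KM estimate of OS at 12 months", and "OS24 will be defined as the KM estimate of OS at 24 months". SAP 4.2.2.3 also reports the number and percentage of patients who have died. It does not say whether a known but undated death is included in that count.

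**The concern.** Kaplan-Meier is unbiased only if a censored patient has the same future risk as those still being followed. Here the reason for censoring is that the patient died. The curve then shares that patient's weight among the survivors, and the expected effect on median OS, OS12 and OS24 is upward.

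The rule also gives opposite event status to patients about whom almost the same is known. If the recorded year is the year of last contact, 1 January falls before last contact. The partial-date rule then dates the death at last known alive + 1 day, so the year adds nothing to the date. Without the year, that same date is available but the death is dropped.

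The cohorts are small (26 or 11 in SARCOMA, 10 in STO), so one patient can be visible in the estimate. The Kaplan-Meier event count may also differ from the reported number of deaths.

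**Working it through.** The plan gives no expected OS, number of deaths or share of undated deaths, so there is no figure of its own to reproduce. The check covers direction and size under stated assumptions.

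**Inputs**

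- Cohort sizes of 26 and 10 evaluable patients (SAP 1.3), with 11 for SARCOMA stage 1.
- Illustrative survival: median OS 9.2 months and 12-month OS 40.5%, from the pediatric pembrolizumab study described in protocol 2.2.1. This is not a planning assumption of the trial. An exponential curve fits both figures: 0.5^(12/9.2) = 0.405. It gives 0.5^(24/9.2) = 0.164 at 24 months.
- Last known alive uniformly 0 to 2 months before death (assumption, based on the 2-monthly survival contacts in protocol section 8).
- Follow-up of 30 months, and one to three undated deaths (assumptions).

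**Step 1: formula.** If a random share q of deaths is censored just before death, the hazard becomes (1 − q) times its true value, and S(t) becomes S(t)^(1−q).

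| q | OS12 (true 40.5%) | OS24 (true 16.4%) | Median (true 9.2 months) |
|---|---|---|---|
| 2% | 41.2% | 17.0% | 9.4 |
| 5% | 42.4% | 18.0% | 9.7 |
| 10% | 44.3% | 19.6% | 10.2 |

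**Step 2: Kaplan-Meier simulation, 6,000 runs per row.** Each cell gives true dates / SAP rule / event at last known alive + 1 day. Medians are averaged over runs where they could be estimated.

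| n | Undated deaths | OS12 (%) | OS24 (%) | Median (months) |
|---|---|---|---|---|
| 26 | 1 | 40.5 / 42.0 / 40.4 | 16.4 / 17.6 / 16.3 | 8.97 / 9.54 / 8.93 |
| 26 | 2 | 40.4 / 43.5 / 40.2 | 16.1 / 18.6 / 16.0 | 8.92 / 10.18 / 8.84 |
| 26 | 3 | 40.6 / 45.1 / 40.2 | 16.3 / 20.2 / 16.2 | 8.98 / 10.82 / 8.87 |
| 10 | 1 | 40.5 / 44.4 / 40.2 | 16.2 / 19.4 / 16.1 | 8.55 / 10.09 / 8.45 |

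The formula agrees. Expected deaths by 30 months are 26 × (1 − 0.5^(30/9.2)) = 23.3, so one undated death is q = 1/23.3 = 4.3%, and 0.405^0.957 = 42.1%, against 42.0% simulated.

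The direction is an expectation and does not hold in every data set. With n = 26 and one undated death, OS12 rose in 66% of runs, was unchanged in about 33% and fell in about 1%. OS24 rose in 92%.

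**Step 3: an example that can be checked by hand.** Take 11 patients, 7 deaths by month 12 and nobody else censored, so true OS12 is 4/11 = 36.4%. If the k-th death is censored instead, OS12 = (12 − k)/11 × 4/(11 − k). For k = 1 this is 40.0%, for k = 4 it is 8/11 × 4/7 = 41.6%, and for k = 7 it is 45.5%.

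**Step 4: longer gaps since last contact.** Undated deaths may arise mainly in patients lost to follow-up. With n = 26 and 10% of deaths undated (about 2.3 patients):

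| Gap before death | OS12 error, SAP rule | OS12 error, event at last known alive + 1 day |
|---|---|---|
| 0 to 12 months | +2.6 points | −1.4 points |
| 0 to 18 months | +2.2 points | −1.7 points |

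Per patient, the SAP rule then adds about 2.6/2.3 = 1.1 or 2.2/2.3 = 1.0 points. The alternative stays closer to the truth, but its downward error is no longer negligible.

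**The case against.** The strongest defence is that this is a pre-specified convention for one special case. Protocol 9.5 leaves the handling of missing data to the SAP. A reader might infer that the SAP holds two rival OS definitions. The documents do not support that: there is one definition and one explicit exception. What stands is that the exception has no stated reason, is absent from SAP section 6 and does not fit the partial-date rule beside it.

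Such patients should also be rare. Date of death is a collected variable for serious adverse events (protocol 8.3.4), deaths go on a Statement of Death page (8.3.12), survival contacts are every 2 months (8.1.2), and lost patients are traced through records, physicians and registries (7.2). This stands, and it limits the point. A reader might infer that OS, OS12 and OS24 will be overstated, perhaps by several points. The documents do not show that any undated death will occur, and any assumed share is outside them.

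A reader might also infer that the death count will disagree with the Kaplan-Meier events. SAP 4.2.2.3 does not say how undated deaths are counted, so the most that can be said is that the two may differ.

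Finally, counting every undated death as an event has its own difficulty. Survival calls are made after the DCO, and deaths after the DCO are censored at the DCO. An undated death first learned of in those calls cannot always be placed before it. This objection stands and shapes the fix.

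**Conclusion.** The point holds in a conditional form. The rule is an unexplained exception to the SAP's own censoring principle and is inconsistent with its partial-date rule. If a patient falls under it, the censoring is informative and the expected bias in median OS, OS12 and OS24 is upward.

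The effect of one such patient on OS12 is about +1.5 points in a cohort of 26 and about +4 points in a cohort of 10. These figures assume exponential survival with 12-month OS near 40%, 30 months of follow-up and last contact 0 to 2 months before death. Longer gaps make the effect smaller. The number of such patients is unknown and probably small.

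OS, OS12 and OS24 are descriptive, with no test attached. The ORR test and the Simon stopping decision are unaffected. The change is worth making because it is cheap and the cohorts are small.

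**What to change.** Replace the last rule of SAP 3.2.3 with the following, applied after the date has been queried:

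1. If the patient is known to have died on or before the DCO (for example, the death was reported by then) and the date is entirely missing, count an OS event at last known alive + 1 day.
2. If the death was first learned of after the DCO and cannot be placed before it, apply a rule stated in advance. One option is to censor at last known alive in the main analysis and count an event in a sensitivity analysis.
3. List the affected patients, and state whether they are included in the death count of SAP 4.2.2.3.
4. Run a sensitivity analysis with the event at the earlier of the date the death was reported and the DCO.

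The cost is a few sentences and a small programming change, since the last-known-alive + 1 day floor already exists for partial dates. The drawback is that the imputed date is early, so OS becomes somewhat conservative. With gaps of 0 to 2 months and one undated death, OS12 is about 0.1 points low at n = 26 and 0.3 at n = 10. It is 1.4 to 1.7 points low in the longer-gap scenarios with 10% of deaths undated. The sensitivity analysis puts the event at a later date and so shows how much this matters.
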